The primary analyses will include all CYP in the ITT sample with complete baseline/outcome data regardless of whether their family is classed as being 'compliant' (i.e. by completing 6+ sessions of MBT-PP). To estimate the impact of the Tavistock programme for CYP from families classed as 'compliant', we will undertake two analyses for the SDQ primary outcome; a per-protocol (or on-treatment) and Compliers Average Causal Effect (CACE) analysis. The on treatment analysis would restrict the Tavistock intervention group to only include CYP from families who received 6+ sessions of MBT-PP and compare SDQ outcomes with the complete CYP sample randomised to receive TAU. To accompany the on-treatment analysis, a descriptive comparison of the compliant, non-compliant CYP / family samples will be presented to examine whether it is reasonable to assume that compliant and non-compliant families are 'similar' (the validity of on-treatment analyses is based on this). If compliant and non-compliant families are systematically different, this provides clear evidence that randomness within the on-treatment analyses has been undermined. The CACE analysis would attempt to address the bias within the on-treatment analysis by adopting an instrumental variable (IV) approach using a two stage Least Squares (2SLS) analysis (Sussman & Hayward. 2010; Tilbrook et al. 2014). The first stage would model the binary compliance measure using the baseline SDQ along with additional variables at the CYP and family levels. This model will be used to generate the predicted compliance for the Tavistock programme. The second stage model will then use the predicted compliance variable in place of the group identifier to generate the CACE estimate for the Tavistock programme. In the event of the on-treatment and CACE estimates being closely aligned, we would favour the reporting of the on-treatment estimate for communicability reasons because it is less abstract / technical compared to CACE. However, if notable differences between the on-treatment and CACE estimates are observed, we would favour the CACE estimate because of this attempts to address the potential bias within on-treatment (i.e. families who comply being different from families that do not comply). STATA IVRegress will be used for this IV approach for estimating CACE.

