Secondary analyses will address the secondary questions of whether, compared to TAU, MBT-PP produces: reduced IPC, lower child perception of IPC, improved parenting style, reduced parent anger expression, improved parent emotional adaptation to the situation, and improved CYP psychological well-being.

Mediation analyses using structural equation modelling will be employed to test whether IPC, lower child perception of IPC, reduced parent anger expression, and improved parent emotional adaptation to the situation are significant mechanisms by which MBT-PP improves CYP adjustment (parent report SDQ scores).

Descriptive statistics will be used to compare the demographics of the sample to the local populations of the LAs. Dropout analyses will be used to assess whether there were systematic differences between participants who were and were not compliant with MBT-PP.

Quantitative data will initially be analysed to establish the extent and nature of any missing data (i.e. MCAR, MCR MNAR). An appropriate imputation solution will be implemented and the ITT analyses will be re-done using this imputed data as sensitivity analyses.

Any parametric test assumptions will then be evaluated and violations to assumptions will be addressed as appropriate (e.g. through data transformations).

Data will be aggregated across the pilot and efficacy studies either pooling the data or using meta-analytic techniques, depending on any design changes that occur from pilot to efficacy, to produce the overall impact estimates of the efficacy study with internal pilot.

All planned statistical analyses will be set out in the Statistical Analysis Plan (SAP) prior to any analysis taking place.

Longitudinal follow-ups

It is possible that the effects of MBT-PP are not seen immediately that the therapy finishes, but take some time to embed into the family system in a way that effects change. We therefore plan to conduct a 3-month follow up. This will take place 3 months from the last session of MBT-PP, or, for those in TAU, 7 months (the length of MBT-PP + 3 months) after the baseline measures. All baseline measures will be repeated.

The analytic procedures employed to analyse the follow up data will be the same as those used to analyse the post-intervention data (but with an additional time point). All analyses will be fully specified in the SAP.

Implementation and process evaluation

Implementation Research Questions (RQs)

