- $\beta_{4..7}$ are the coefficient estimates for the four family-level dummy variables.

² This because centring the CYP level scores around their cluster (family) mean is an orthogonal transformation, CYP scores are placed relative to their family mean and so will not share any variance ($r = 0$).

- ϑ'_j and ε'_{ij} are random effects that remain at the school and pupil levels and are assumed to be distributed normally in the population with zero means, variances σ_c^2 and τ_c^2 respectively, and for these variances to be conditionally uncorrelated.

The estimate of impact will be standardised as an effect size by dividing by the standard deviation obtained from the variance partition estimates for the empty/null model described in equation 2.1:

$$[2.1] \quad Y_{ij} = \beta_0 + \vartheta_j + \varepsilon_{ij}$$

Where:

- β_0 is the constant term for the empty model and represent the mean mothers reported SDQ-TD for CYP at T2 (16 weeks following minimisation).
- ϑ_j and ε_{ij} are random effects at the school and pupil levels and are assumed to be distributed normally in the population with zero means, variances σ^2 and τ^2 respectively.

Table 5 summarises the ITT analysis for the mothers SDQ-TD primary outcome described in equation 2.0.

Table 5. Example analysis model for mothers SDQ-TD primary outcome (RQ1a)

Analysis and Sample	Level 1 (CYP) Covariates	Level 2 (Family) Covariates	Outcome Variable
Null/Empty model			CYP level mothers SDQ-TD (raw) score at T2 (16 weeks following minimisation)
Final Model	Mothers SDQ-TD score at T1/baseline (Centred around family mean)	Mean mothers SDQ-TD score at T1/baseline (Centred around grand mean) Group membership (MBT or TAU) Four Minimisation Dummy Variables: CYP ages (2); parental ethnicity (1), relationship status (1);	CYP level mothers SDQ-TD (raw) score at T2 (16 weeks following minimisation)

The empty model is described by equation 2.1 and the final model by equation 2.0. The impact of the MBT-PP programme (compared with TAU) amongst parents experiencing IPC on

mothers SDQ-TD scores will be estimated using the coefficient for the group membership family-level covariate included in the final model (β_1 in equation 2.0). Impact will be standardised into an effect size by dividing the β_1 coefficient shown by the unconditional standard deviation from the null/empty model described in equation 6.0 below.

Secondary outcome analysis

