Table 4 above lists a total of 35 secondary outcomes. For all 35 secondary outcomes, an ITT approach will be taken.

For the analysis of all secondary outcomes, an estimate of impact will be obtained from a hierarchical linear model described in equation 3.0:

$$[3.0] \quad Y_{ij} = \beta_0 + \beta_1 T_j + \beta_2 (X_{ij} - \bar{X}_j) + \beta_3 (\bar{X}_j - \bar{X}) + \beta_{4..7} [MIN DUM]_j + \vartheta_j + \varepsilon_{ij}$$

Where:

- Y_{ij} is secondary outcome score for CYP i in family j at T2 (16 weeks following minimisation).
- T_j is the family-level group identifier which will take the value 1 (=MBT) or zero (=TAU)
- β_1 is the coefficient that estimates the difference between the MBT and TAU groups adjusted for baseline scores and mimimisation variables; i.e. $(MBT - TAU)_{adjusted}$
- X_{ij} is the baseline score for the secondary outcome for CYP i in family j at T1/baseline centred around \bar{X}_j , the family-level mean (i.e. $(X_{ij} - \bar{X}_j)$)
- \bar{X} is the family-level grand mean for the secondary outcome and used to centre \bar{X}_j , the family-level mean (i.e. $\bar{X}_j - \bar{X}$)
- $[MIN DUM]_j$ is the collection of four family-level dummy variables used in the minimisation; ages of CYP in family (two variables); whether one parent was not White British (one variable) and relationship status (one variable).
- $\beta_{4..7}$ are the coefficient estimates for the four family-level dummy variables.
- ϑ_j and ε'_{ij} are random effects that remain at the school and pupil levels and are assumed to be distributed normally in the population with zero means, variances σ_c^2 and τ_c^2 respectively.

Table 6 summarises the ITT analysis for the fathers SDQ-TD secondary outcome as an example, a similar approach will be used for all secondary outcomes at T2.

Table 6. Example analysis model for fathers SDQ-TD primary outcome (RQ1b)

Analysis and Sample	Level 1 (CYP) Covariates	Level 2 (Family) Covariates	Outcome Variable

Empty model			CYP level fathers SDQ-TD (raw) score at T2 (16 weeks following minimisation)
Final Model	Fathers SDQ-TD score at T1/baseline (Centred around family mean)	Mean fathers SDQ-TD score at T1/baseline (Centred around grand mean) Group membership (MBT or TAU) Four Minimisation Variables: CYP ages (2), parental ethnicity (1), relationship status (1).	CYP level fathers SDQ-TD (raw) score at T2 (16 weeks following minimisation)

Subgroup analyses

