Null/Empty Models Two Subsamples: Pilot & Stage 2 evaluations.			CYP level mothers SDQ-TD (raw) score at T2 (16 weeks following minimisation)
Subgroup Impact Models Two Subsamples: Pilot & Stage 2 evaluations.	Mothers SDQ-TD score at T1/baseline (Centred around family mean)	Mean mothers SDQ-TD score at T1/baseline (Centred around grand mean) Group membership (MBT or TAU) Four Minimisation Variables: CYP ages (2), parental ethnicity (1), relationship status (1)	CYP level mothers SDQ-TD (raw) score at T2 (16 weeks following minimisation)

Longitudinal follow-up analyses

The T3 3 month follow up data provides 18 of the secondary outcome variables (see Table 4). As specified above, these will be subjected to the same analyses as the primary outcome variable.

Testing the theory of change mechanisms

To examine the causal mechanisms proposed in the theory of change we will undertake multigroup structural equation modelling (SEM) comparing the model in Figure 1 across the MBT and TAU groups. The initial model will be undertaken using the post-intervention measures of the variables included in Figure 1.

Figure 1. Proposed causal model for SEM analysis with child internalising and externalising behaviours (mothers' SDQ-TD) as the final latent variable in the causal chain on post-intervention measures.

[figure not shown]
[figure not shown]

Figure 2. Proposed causal model for SEM analysis for separated parents, including the parental emotional adaptation measure.

Using the data from separated families only, we will also test the model in Figure 2, which treats emotional adaptation to relationship dissolution as an additional mediator, alongside anger expression. Again, this will be undertaken using the post-intervention measures.

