These latter models will be tested in the same way as outlined above for the models with child internalising and externalising behaviours as the final latent variable in the causal chain.

Imbalance at baseline

The characteristics of the MBT and TAU group families and CYP as measured prior to randomisation will be compared. At the CYP level, this will include the T1 mothers SDQ-TD primary outcome and X secondary outcomes, ethnicity, age, gender, EAL and SEND status. At the family level this will include the three minimisation variables (relationship status, CYP ages and parental ethnicity) along with family size and the aggregated primary and secondary outcomes. For scale/continuous variables, means and standard deviations for the MBT and TAU groups will be reported and the difference converted into a Hedges g effect size by dividing the mean difference (MBT – TAU) by the pooled standard deviation. For categorical variables, counts and percentages will be reported.

The analyses of balance at baseline will be replicated for the subsample of CYP included in the final impact analysis for the primary outcome; a complete case subsample. In the case of very low attrition, baseline and complete case analyses should reflect each other. However, as attrition increases, differences are likely to be seen. These analyses will inform the missing data analyses described in the next section.

Missing data

The amount of missing outcome data for the mothers SDQ-TD primary outcome will be summarised, and reasons for missing data discussed in the report, where available. If greater than 5% of CYP have missing mothers SDQ-TD, multi-level logistic regression will be used to model presence or absence of the primary outcome including all available CYP and family-level baseline data as fixed effects, and family as a random effect. Significant variables and possible reasons for the missing data will be discussed in the report.

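### The T3 impact estimates make no use of T2 scores, which costs a little precision if T3 is incomplete and leaves bias uncorrected if T2-related loss differs by arm

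*SAP*

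**What the plan says.** - **T3 model.** SAP, Longitudinal follow-up analyses: "The T3 3 month follow up data provides 18 of the secondary outcome variables". It continues: "As specified above, these will be subjected to the same analyses as the primary outcome variable". SAP, Secondary outcome analysis, confirms the scale: "Table 4 above lists a total of 35 secondary outcomes", that is 17 at T2 and 18 at T3.
- **What that model contains.** SAP, Primary outcome analysis, equation 2.0 and Table 5: one outcome time, arm, four minimisation dummies, the child's T1 score centred on the family mean, and the family-level term "Mean mothers SDQ-TD score at T1/baseline (Centred around grand mean". There is no T2 term and no repeated-measures structure.
- **Analysis set.** Protocol, Analysis: "The primary analyses will include all CYP in the ITT sample with complete baseline/outcome data".
- **Missing data.** SAP, Missing data, opens with "The amount of missing outcome data for the mothers SDQ-TD primary outcome will be summarised". The drop-out model and the imputation are then written for T2 mothers' SDQ, with the baseline-balance variables as predictors. Imputation is run only if a covariate predicts missingness significantly.
- **Protocol on follow-up.** Protocol, Longitudinal follow-ups, says the procedures will be the same as "those used to analyse the post-intervention data (but with an additional time point"), with the detail left to the SAP.
- **Only joint use of T2 and T3.** SAP, Testing the theory of change mechanisms: a conditional re-test of the structural equation models with T2 mediators and T3 outcomes. That is not the T3 impact estimate.

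**The concern.** T3 is where the trial looks for delayed or lasting effects; the protocol's reason for the follow-up is that change may take time to settle into the family. Every measure is also collected at T2, and T2 is likely to be the best available predictor of a missing T3 value. A model that sees only T1 and T3 discards that information for anyone who attends T2 and misses T3.

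Two things follow, each under a condition. If some T3 values are missing, precision is lost. If T3 loss is related to the T2 score differently in the two arms, the T3 contrast is biased, and adjusting for T1 does not remove it. Such a difference is possible here. T3 is timed from the last therapy session in MBT-PP but from baseline in TAU. Clinical assessment after allocation, with possible onward referral, happens only in MBT-PP. Protocol Appendix A, criterion 9, itself asks whether attrition differs between arms.

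**Working it through.** **1. Reproduce the plan's precision figure.** Inputs from SAP, Sample size calculations: P = 0.50, ICC = 0.27, R² = 0.61 (family) and 0.75 (child), n = 1.4, m = 6, two-sided 0.05, power 0.80. Equation 1.0 with J = 250, df = 250 − 6 − 2 = 242:

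- variance term: 0.27×0.39/250 + 0.73×0.25/(1.4×250) = 0.000421 + 0.000521 = 0.000943
- SE = 2×√0.000943 = 0.0614; multiplier 2.813; MDES = 0.173 (SAP: 0.17)
- J = 225 gives 0.182 (SAP: 0.18 at 10% attrition); J = 200 gives 0.193 (SAP: 0.19 at 20%)

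The SAP's figures reproduce. They are for T2 mothers' SDQ; the documents give no power or precision figure for T3. Below, the same parameters are assumed to hold at T3.

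**2. Precision.** Let ρ be the T2-T3 correlation given T1, and d the fraction missing T3 at random, with everyone seen at T2. Then SE(joint)/SE(T3 only) = √(1 − ρ²d). Neither ρ nor d at T3 is in the documents; 10% and 20% are the SAP's overall attrition scenarios, borrowed here.

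| ρ (assumed) | d = 10%: ratio (MDES 0.182 becomes) | d = 20%: ratio (MDES 0.193 becomes) |
|---|---|---|
| 0.3 | 0.9955 (0.181) | 0.991 (0.192) |
| 0.5 | 0.9874 (0.180) | 0.9747 (0.188) |
| 0.7 | 0.9752 (0.178) | 0.9497 (0.184) |

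The SE reduction is about 0.5-2.5% at 10% loss and 1-5% at 20%. At d = 0 the ratio is 1. If some of those missing T3 also missed T2, the gain is smaller.

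**3. Bias when T2-related loss exists in MBT-PP only.** The bias of the T3-only contrast is ρ × σ × Δ. Here σ is the residual SD given T1: σ² = 0.27×0.39 + 0.73×0.25 = 0.2878, so σ = 0.536. Δ is the mean standardised T2 residual among MBT-PP participants still seen at T3. With logistic loss at 0.5-0.8 log-odds per residual SD (assumed), numerical integration gives Δ from −0.049 to −0.075 at 10% loss and −0.096 to −0.145 at 20%. With ρ = 0.5-0.7 (assumed):

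- 10% loss: from 0.5×0.536×0.049 = 0.013 to 0.7×0.536×0.075 = 0.028 SD
- 20% loss: from 0.5×0.536×0.096 = 0.026 to 0.7×0.536×0.145 = 0.054 SD

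Rounded outward, that is 0.01-0.03 and 0.03-0.06 SD. The sign favours MBT-PP if families with poor T2 scores are the ones lost, and goes against it if families who did well stop responding.

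**4. Bias when the relation is the same in both arms.** Δ is then the same in each arm and cancels.

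**5. Cross-check by simulation.** 2,000,000 independent children, T1 correlation 0.75, loss odds ratio 2 per SD of T2, ρ = 0.5-0.7 (all assumed), true effect 0 or −0.20 SD:

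| Relation of T2 score to T3 loss | T3-only bias, 10% loss | T3-only bias, 20% loss |
|---|---|---|
| Same in both arms | about 0 | at most about 0.004 in size |
| MBT-PP only | −0.01 to −0.02 | −0.03 to −0.04 |
| Opposite in the two arms | −0.03 to −0.04 | −0.06 to −0.08 |

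The joint T2/T3 estimate was within about 0.002 SD of the truth in every case.

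**The case against.** A separate baseline-adjusted analysis at each time point is valid and widely used. All 18 T3 results are secondary and unpowered, and the primary T2 analysis is untouched. With complete T3 data, a joint model with time-specific effects gives essentially the same T3 contrast. At the attrition the plan considers, the precision gain is a few percent at best. All of this stands, and it limits the point to an improvement.

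Three stronger readings are tempting and are not supported.

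- **That T3 results are biased whenever T3 loss depends on T2.** A relation shared by both arms leaves the contrast essentially unbiased (working, steps 4 and 5). Only a difference between arms matters, and the documents give no evidence of one.
- **That the SAP breaks a protocol commitment.** The phrase "but with an additional time point" can mean applying the same model at one more time. It does not promise a repeated-measures model.
- **That the SAP prescribes complete cases only at T3.** The complete-data statement is about the primary analysis, and treating T3 like the primary outcome could carry the conditional imputation over. The SAP is silent rather than explicit. That reading does not close the gap, because the imputation section names only baseline predictors and T2 would still be unused.

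**Conclusion.** The point holds in a limited form. By cross-reference, the T3 impact model uses T1 alone, and no named imputation model uses T2. The cost is a standard error that could be about 0.5-2.5% smaller at 10% T3 loss and 1-5% smaller at 20%. There is also exposure to a bias of about 0.01-0.03 SD (10% loss) or 0.03-0.06 SD (20% loss) if T2 score and T3 loss are related in MBT-PP only. Against the SAP's MDES of 0.17, the upper range is 0.03/0.17 = 18% to 0.06/0.17 = 35%, enough to colour a claim of a lasting effect. If the relation is the same in both arms the bias is about zero; if T3 is complete there is nothing to gain.

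T3 loss, the T2-T3 correlation and the strength of drop-out are assumptions throughout. The change is worth making because it uses data already collected, but it does not bear on the primary result.

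**What to change.** Keep equation 2.0 as the primary T2 analysis. For each outcome, take the T3 arm contrast from one joint model of T2 and T3 that includes everyone with either time point. Fixed effects: arm, time, arm × time, T1 score × time, and minimisation dummies × time. The covariance structure should follow the type of outcome:

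- **Four child-level outcomes** (mothers' and fathers' SDQ, child well-being, child-perceived conflict): family random intercept and time effect, so that family variance may differ by time, plus unstructured child-level residuals.
- **Fourteen parent-report outcomes** (seven scales or subscales, each for mother and father), taken as one record per family at each time: an unstructured 2×2 residual covariance and no separate family intercept. Adding one would ask for four parameters from two variances and one covariance.

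An acceptable alternative is to impute T3 separately by arm with the T2 score in the imputation model, and then fit the T3 model. T2 should not be a covariate in the T3 impact model itself, because it is measured after randomisation.

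The cost is SAP wording and slightly more complex code. No new data are needed.

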To address not only whether the intervention works, but also how the intervention works, we will also test the exploratory mediation models depicted in Figure 1 and Figure 2.

RQ9 Is the effect of MBT-PP (compared to TAU) on externalising and internalising behaviours in children aged 8-14 (as measured by the SDQ 'difficulties' scale) mediated by parent mentalising, parent anger expression, parent report IPC, child perception of IPC, parenting style, or parent emotional adaptation?

RQ10 Is the effect of MBT-PP (compared to TAU) on wellbeing in children aged 8-14 (as measured by the Stirling Children's Well-being Scale) mediated by parent mentalising, parent anger expression, parent report IPC, child perception of IPC, parenting style, or parent emotional adaptation?

Figure 1. Examining the mechanisms by which MBT-PP may improve children’s externalising and internalising behaviours

[figure not shown]
[figure not shown]

Figure 2. Examining the mechanisms by which MBT-PP may improve children’s psychological well-being

Design

Table 2. Trial design

Trial design, including number of arms		Pragmatic two arm cluster RCT
Unit of randomisation		Family
Minimisation variables (if applicable)		Age group (all CYP aged 8-11 / all CYP aged 12-14 / CYP aged 8-11 and 12-14), Minority ethnic group status of one or both parents (yes / no), relationship status (separated/intact)
Primary outcome	variable	a) Child internalising and externalising
	measure (instrument, scale, source)	a) Parent reported SDQ, total difficulties scale (Goodman, 1997)
Secondary outcome(s)	variable(s)	
 b) Child psychological well-being c) Parent report IPC d) Child perception of IPC e) Parent anger f) Parent mentalising capacity g) Parenting style h) Parent emotional adaptation to separation (separated parents only)
	measure(s) (instrument, scale, source)	
 b) Stirling Children’s Well-being Scale (Liddle & Carter, 2015) c) O’Leary-Porter Scale (Porter & O’Leary, 1980) d) Perceptions of Interparental Conflict-Intensity/Frequency Scale (PIC-I/F) (Kline, Wood & Moore, 2003) e) Dimensions of Anger Reactions- Revised (DAR-R; (Nederlof, Hovens, Muris & Novaco, 2009) f) Parental Reflective Function Questionnaire (Luyten et al., 2009) g) Parenting Scale Short Form (PS-8) (Kliem et al., 2019), a short form of the Parenting Scale (Arnold et al., 1993) h) Emotional Adaptation to Relationship Dissolution Assessment (Millings et al., 2020)

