Structural equation modelling (SEM) is the most appropriate technique with which to test these models because unlike path analysis it enables us to estimate measurement error within the model. The SEM analyses will be conducted using the Lavaan package in R. MBT and TAU groups will be included in the analyses together with the initial analysis fitting the same model to both groups with all parameters set to be free and model parameters being generated for each group separately. Fit of all models tested will be appraised using commonly used fit indices. Fit for the whole model and the models for each group will be determined with chi-square, CFI, RMSEA, SRMR, and AIC. Following Hu and Bentler (1999) the following criteria will be used to determine good fit (CFI > .95; RMSEA < .06; and SRMR < .08).

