If the assumption of measure invariance is upheld, we will look to compare latent means across group with a particular focus on the mentalising latent variables as these are the key targets of the MBT intervention. This would be undertaken by restricting the models to have equal means in the mentalising latent variables and then conducting likelihood ratio tests to compare this constrained model with the model where the means are free to vary. If the likelihood ratio test is not significant then this would suggest that groups do not differ in terms of these latent means. We would also compare the regression coefficients from the mentalising latent variables to the anger expression latent variable in a similar way.

We will first utilise the above method to test a model featuring post-intervention SDQ-TD score (mothers) as the final endogenous variable in the causal chain. We will then test the same models with child well-being score at post-intervention as the final endogenous variable (figures 3 and 4). We will repeat this whole process using fathers' SDQ-TD scores. We will run these SEM models even in the absence of a main effect on each final endogenous variable, because it is possible to detect indirect effects in the absence of a direct effect, and indeed important to do so to provide information as to why the main effect is present or not (O'Rourke & Mackinnon, 2018).

Additionally, if there are sufficient responses from the three month follow-up testing for the primary (child internalising and externalising behaviours) and secondary (child psychological well-being) measures we will re-test the models in Figures 1 & 3 (and if possible Figures 2 & 4) but with replacing the post-intervention measures of these primary and secondary outcome with the three-month follow-up measures of these variables. This potentially enables us to test whether changes to mentalising, anger expression, interparental conflict and parenting style at time 2 predicts child behaviour and well-being at follow-up and thus potentially further supporting any causal relationships established from the post-intervention SEM modelling.

Figure 3. Proposed causal model for SEM analysis with the secondary outcome measure of child psychological well-being.

[figure not shown]
[figure not shown]

Figure 4. Proposed causal model for SEM analysis for separated parents with the secondary outcome measure of child psychological wellbeing, including the parental emotional adaptation measure.

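### As specified, the SEM compares mentalising means and one path across arms but never forms an indirect effect of allocation, so exploratory RQ9 and RQ10 go unanswered

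*SAP*

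**What the plan says.** **The questions.** In the protocol's Mechanisms of Action Research Questions, RQ9 opens "Is the effect of MBT-PP (compared to TAU) on externalising and internalising behaviours in children aged 8-14" and asks whether that effect is "mediated by parent mentalising, parent anger expression, parent report IPC, child perception of IPC, parenting style, or parent emotional adaptation". The next question, "RQ10 Is the effect of MBT-PP (compared to TAU) on wellbeing in children aged 8-14", asks the same for the Stirling scale. The protocol calls these mediation models exploratory. Its Analysis section promises mediation analyses by SEM, naming four of the six variables as mechanisms to be tested.

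**The analysis.** The SAP restates RQ1 to RQ8 only. Mechanisms are covered under Testing the theory of change mechanisms:

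- Arm is the grouping variable: "we will undertake multigroup structural equation modelling (SEM) comparing the model in Figure 1 across the MBT and TAU groups".
- Timing: "The initial model will be undertaken using the post-intervention measures of the variables included in Figure 1".
- The initial analysis is described as "fitting the same model to both groups with all parameters set to be free and model parameters being generated for each group separately".
- Configural, metric and scalar invariance are then tested.
- If invariance holds, latent means are compared across arms, chiefly for mentalising. In addition: "We would also compare the regression coefficients from the mentalising latent variables to the anger expression latent variable in a similar way".
- If invariance fails, the arms are modelled separately and no SEM parameter is directly compared between them.
- The section justifies running the models by saying that indirect effects can be found without a direct effect. It defines no indirect effect, product of paths or interval.
- If there are enough three-month responses, the models are re-run with T2 mediators and T3 child outcomes.

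Separately, the mediators are secondary outcomes in SAP Table 4. Each has its own baseline-adjusted ITT model (Secondary outcome analysis, equation 3.0).

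**The concern.** A mediation question concerns the part of the treatment effect that passes through an intermediate variable. Answering it needs two linked quantities: how far allocation moves the mediator, and how far the mediator then moves the outcome. The SEM section estimates pieces of each but does not join them.

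The planned results are also easy to misread:

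- Equal mentalising-to-anger coefficients in the two arms do not argue against mediation.
- Unequal coefficients show moderation.
- Good fit and significant paths within an arm can arise when MBT-PP moved no mediator.

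The final report could therefore present within-arm associations as evidence of how MBT-PP works.

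Three further gaps weaken the same section. No T1 mediator or outcome score is described as entering the SEM, although the text reads T2 mediator levels as changes. Clustering of children in families is handled in the impact and CACE models but not mentioned for the SEM. And the between-arm SEM comparison lapses if invariance fails.

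**Working it through.** **Inputs.** The SAP gives 250 families, 125 per arm. As a check on that design, SAP equation 1.0 with J = 250, m = 6, n = 1.4, ICC 0.27, R² 0.61 (family) and 0.75 (child) gives

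- family term: 0.27 × 0.39 / 250 = 0.000421
- child term: 0.73 × 0.25 / (1.4 × 250) = 0.000521
- MDES = 2.813 × 2 × √0.000943 = 0.173, against the SAP's 0.17.

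The documents state no effect size or power for the mediation models, so the path values below are assumptions.

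**What each planned test responds to.** A chain allocation (T) → mentalising (M) → anger (A) → SDQ (Y) was simulated with one record per family, 125 per arm and 4,000 runs per scenario:

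- M = a·T + e
- A = (b1 + d·T)·M + √(1 − b1²)·e
- Y = b2·A + √(1 − b2²)·e

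with b1 = b2 = 0.4 and d = 0 unless stated. With d = 0, the true indirect effect is a·b1·b2; for a = 0.5 it is 0.5 × 0.4 × 0.4 = 0.08 SD. The first three columns represent the tests and paths the SAP would produce. The last enters allocation as a predictor and requires all three links to be significant.

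| Scenario | Mediation? | Coefficient equality | Mean contrast | Within-arm chain | Allocation chain |
|---|---|---|---|---|---|
| a = 0.2 | yes | 4.9% | 35.6% | 98.8% | 36.0% |
| a = 0.35 | yes | 5.2% | 77.6% | 98.5% | 77.8% |
| a = 0.5 | yes | 5.0% | 98.0% | 99.2% | 98.0% |
| a = 0 | no | 5.8% | 5.1% | 98.6% | 5.2% |
| a = 0, d = 0.3 | no | 71.9% | 5.0% | 98.8% | 5.0% |
| a = 0.5, b2 = 0 | no | 5.2% | 97.9% | 5.6% | 5.2% |
| a = 0.5, b1 = 0 | no | 4.9% | 97.5% | 5.1% | 4.9% |

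- The coefficient test stays near 5% when mediation is real and rejects in 72% of runs when there is moderation without mediation.
- The within-arm chain looks the same with mediation (98.5 to 99.2%) and without any effect on mentalising (98.6%).
- The mean contrast detects the first link but also rejects in about 98% of runs when a later link is absent.
- Only the linked chain separates the mediation rows from the others.

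**Clustering.** Suppose the SEM uses one row per child and parent scores are repeated across siblings; the SAP states neither. Treating rows as independent then understates standard errors of parent-level paths by:

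- equal clusters of 1.4: 1 − 1/√1.4 = 15%
- 60% one-child and 40% two-child families (assumed): E[n²]/E[n] = 2.2/1.4 = 1.57, and 1 − 1/√1.57 = 20%.

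Paths involving child-reported conflict or child outcomes would be affected less, because those scores are not simple copies across siblings.

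**The case against.** The plan contains more than a comparison of associations. The latent-mean test of mentalising is, under randomisation, a treatment-to-mediator contrast. The equation 3.0 models give a baseline-adjusted arm effect on each mediator. A reader could set these beside the within-arm paths and judge mediation informally. This stands in part: the ingredients exist. But the SAP gives no rule for joining them, no size or interval for the result, and no link between the ITT models and the SEM.

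Several stronger readings are tempting, and the documents do not support them:

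- *Multigroup SEM cannot address mediation.* The limit lies in the analysis as written. With a mean structure, the arm difference in mediator means can be combined with the paths.
- *Complete mediation would be missed because slopes are equal.* That is true of one of the two contrasts. The mean contrast would respond to the first link.
- *An MBT-PP that moved no mediator would go unnoticed.* The ITT models address that directly.
- *Everything is cross-sectional at T2.* A T3-outcome re-test is planned, though it depends on response and adds no allocation path or baseline score.
- *Noninvariance removes every arm comparison.* It removes the SEM comparisons; the ITT ones remain.
- *Standard errors are 20% too small.* That is the upper end of a range resting on unstated assumptions.

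The path diagrams are not available in the text reviewed, so a drawn treatment node cannot be excluded. It would not help: within each arm allocation is constant, so its path could not be estimated in the model described.

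**Conclusion.** The point holds for the analysis as specified. The latent-mean test and the ITT models supply the treatment-to-mediator half, and the within-arm paths supply associations between mediators and outcome. No planned quantity is the indirect effect that RQ9 and RQ10 ask about. Following the SAP exactly would leave both unanswered, while producing results that could be read as answers.

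The simulation rests on assumed paths, no measurement error, no sibling clustering and no attrition. It shows what each test responds to and is not an estimate of the trial's power. The structural conclusion needs only the text.

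Severity is moderate: this should be fixed. Exploratory status excuses low power, but not leaving out the quantity in question. The primary ITT analysis is untouched.

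**What to change.** Rewrite the SEM section of the SAP as follows:

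1. Fit a pooled SEM with allocation as an exogenous predictor of the mediators and the child outcome, or form the equivalent contrast from the multigroup mean structure.
2. Adjust for T1 mediator and outcome scores and the minimisation factors.
3. State the unit of analysis and use family-clustered standard errors.
4. Report each specific indirect effect and the total, with a cluster-bootstrap or Monte Carlo 95% CI.
5. Base any temporal claim on the planned T2-mediator, T3-outcome model.
6. Keep invariance testing as a measurement check and state what will be reported if it fails.
7. Say that mediator-to-outcome paths are not protected by randomisation. Baseline adjustment reduces confounding of those paths but does not remove it.

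RQ9 and RQ10 should also be restated in the SAP. If the sponsor prefers to keep the present analysis, the SAP should withdraw these two questions and label the SEM as associational. The cost is one rewritten section and revised model code, with no new data or software.
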